1 LIST OF ABBREVIATIONS

Abbreviation	Definition
ACC	American College of Cardiology
ADHF	Acute Decompensated Heart Failure
AE	Adverse Event
AHA	American Heart Association
BMP	Basic Metabolic Panel
BUN	Blood Urea Nitrogen
CRF	Case Report Form
DSMB	Data Safety Monitoring Board
eGFR	Estimated Glomerular Filtration Rate
ER	Emergency Room
FDA	Food and Drug Administration
HF	Heart Failure
HFpEF	Heart Failure with preserved Ejection Fraction
HFrEF	Heart Failure with reduced Ejection Fraction
HIPAA	Health Insurance Portability and Accountability Act
ICF	Informed Consent Form
ICH	International Conference on Harmonization
IND	Investigational New Drug
IP	Investigational product
IRB	Institutional Review Board
IV	Intravenous
NT-proBNP	pro-B-type natriuretic peptide
SEMC	St Elizabeth's Medical Center
SAR	Suspected advanced reactions
NYHA	New York Heart Association
SQ	Subcutaneous

2 EXECUTIVE SUMMARY

SYNOPSIS	
PROTOCOL TITLE	An Open Label, Descriptive Study to Evaluate the Clinical Utility of a Novel Formulation of Furosemide Delivered Subcutaneously in Patients Presenting with Early Signs of Fluid Overload
PROTOCOL NUMBER	Version 4.02
INVESTIGATOR	[name] Director Advanced Heart Failure Program Associate Professor of Medicine, Tufts University School of Medicine. St. Elizabeth's Medical Center (SEMC) [name]
INVESTIGATIONAL PRODUCT	Furosemide Injection, 8 mg/mL, (total dose =80 mg) administered subcutaneously by the sc2Wear Furosemide Infusor using a biphasic profile with 30 mg over the first hour and then as 12.5 mg per hour over the subsequent 4 hours. Participants may be prescribed a total of 3 days initial treatment followed by an optional additional 4 days of sc2Wear furosemide treatment based on initial clinical response.
STUDY OBJECTIVES	The Objectives of this study are: 1.) Evaluate the clinical effect of sc2Wear furosemide Infusor in the in-home management of mild to moderate decompensated heart failure. 2.) Evaluate the safety and tolerability of sc2Wear furosemide Infusor in the in-home management of mild to moderate decompensated heart failure.
STUDY ENDPOINTS	Efficacy • The treatment effect will be described as:

	
 • % weight loss between enrollment/screening compared to Post Visit #1 and Post Visit #2 • Reduction in pro-BNP between enrollment/screening compared to Post Visit #1 and Post Visit #2 • Proportion of patients requiring additional 4 days of diuresis based on a set of pre-defined criteria. • % of patients alive 30 days post enrollment • % of patients without hospitalization for worsening HF within 30 days after enrollment • % of patients without a significant HF related medical events within 30 days after enrollment. 
Safety
 
 • The safety of the sc2 Wear furosemide Infusor drug-device combination will be assessed by the incidence of adverse events. • Discontinuation due to presence of skin reaction to drug or device/adhesive.
STUDY DESIGN & DURATION	
Study Design:
 
This is a prospective, open-label, descriptive two-phase study to evaluate the clinical effectiveness of a novel formulation of furosemide delivered by subcutaneous administration.
 
In the first phase of the study (Pilot Phase) the practicality and safety of the novel in-home treatment alternative will be evaluated in 20 patients presenting with mild to moderate decompensated heart failure to the cardiology service at St Elizabeth's Medical Center (SEMC) at Brighton, Massachusetts.
 
After completion of the first phase, the representatives of the sponsor and scPharmaceuticals will convene to review the

	
experience and results and consider any adjustments to the study or workflow before commencing the Evaluation Phase of the study in which an additional 40 patients will be recruited. The Evaluation Phase may involve participation by other Steward Health Care System hospitals. Adjustments to the study procedures are subject to IRB review and approval.
 
Participants will be treated daily for 3 consecutive days at home after an assessment in the cardiology clinic. Patients will be homebound during the episode of care for decompensated heart failure. Patients will be visited daily by Steward Home Care and Hospice for home health nursing services. In the evening, participants will have the opportunity to supplement diuresis with their usual oral diuretic dose.
 
Patients will be evaluated by a cardiologist at SEMC within 24 hours after the 3rd dose of sc2Wear furosemide. If a patient was found to have satisfactorily responded but requires additional parenteral diuretics an additional 4 days may be prescribed for a total of 7 consecutive treatments.
 
Additionally, up to three sc2Wear furosemide at home treatments may be used as authorized by the treating physician in case the patient experience worsening of heart failure from day 7 to up to 30-days after enrollment.
 
Response will be based on the weight loss, decrease in pro-BNP, or improvement in the dyspnea scale. If additional units are prescribed, patients will be re-evaluated by a cardiologist within 24 hours after the last dose of sc2Wear furosemide. Participants will require a final follow up with a cardiologist at 30-33 days after the start of the study for a post treatment interview and assessment.
 
The protocol is subject to IRB review and approval. The study will be conducted under an Investigator-Initiated Investigational New Drug (IND) Application.

STUDY PROCEDURES	
Screening Phase:
 
The cardiology service will screen patients with mild to moderate fluid overload. Patients who present with other serious or life threatening condition for which hospitalization would be indicated are excluded. Women of child bearing potential will be screened for pregnancy with a urine pregnancy

test. Eligible participants will be educated on device preparation, placement, removal and care in accordance with the Instructions of Use Manual. The screening phase includes evaluation of the home situation to ascertain that sufficient support is or can be made available for at home treatment as an alternative to inpatient care. In appropriate settings, lay caregiver will also be trained.

Pilot Phase.

Patients will be visited daily by Steward Home Care and Hospice for home health nursing services in accordance with standard procedures. Nursing services will include checking vitals, obtaining blood samples and evaluation for clinical improvement or worsening. The first visit will be performed within 24 hours after enrollment.

The first sc2Wear Infusor will be prepared and placed on the patient as part of the training. The patient will go home with the sc2Wear furosemide Infusor in place on the abdomen to be activated upon arrival at home. Participants will be treated with the sc2Wear furosemide Infusor daily for 3 consecutive days at home. Participants will be evaluated by the cardiology service of SEMC within 24 hours after the 3rd dose of sc2Wear furosemide. If a patient was found to have responded satisfactorily but requires additional parenteral diuretics an additional 4 days may be prescribed for a total of 7 consecutive treatments. If additional units are prescribed patients are to be evaluated the cardiology service of SEMC within 24 hours after the last dose of sc2Wear furosemide Infusor.

If the subject requires further parenteral diuresis after the 7 days of at home treatment, they will be converted to usual care at that time, which may require inpatient care. Participants will be instructed to record daily morning weights during and after treatment until the second post treatment evaluation.

Interim clinic visits and laboratory assessments may be required based on clinical considerations.

The following parameters will be studied at Baseline and follow-up treatment visits.

	
 • Body Weight • Vital signs • HF Physical examination • Dyspnea scale • Routine laboratory panel (incl. electrolyte, pro-BNP) • Adverse events • Injection site assessment 
Participants will visit the clinic 30 ± 3 days after the start of the study for a post treatment evaluation.
 
Evaluation Phase
 
The Evaluation Phase mirrors the Pilot Phase except that attempts will be made to test pre-defined clinical care paths based on the lessons of the Pilot Phase. Up to two additional Steward Health Care sites may participate in the Evaluation Phase.

SC2WEAR TREATMENT	
Novel Furosemide Injection formulation at neutral pH, 8 mg/mL, (total dose =80 mg) administered subcutaneously by means of the sc2Wear Infusor as 30 mg over the first hour and then as 12.5 mg per hour over the subsequent 4 hours.
 
Participants will be treated for 3 sequential days with one dose of sc2Wear Furosemide Infusor (80mg) daily. It is generally recommended that the sc2Wear infusor be applied in the morning. Oral diuretics should be continued concomitantly
 
If a patient was found to have satisfactorily responded but requires additional parenteral diuretics an additional 4 days may be prescribed for a total of 7 consecutive treatments.
 
Additionally, up to three sc2Wear furosemide at home treatments may be used as authorized by the treating physician in case the patient experience worsening of heart failure from day 7 to up to 30-days after enrollment.
 
(Rescue Treatment).

NUMBER OF SUBJECTS	60 (20 in Pilot Phase, 40 in Evaluation Phase)
NUMBER OF SITES	Pilot Phase: St Elizabeth's Medical Center Evaluation Phase: Up to three hospitals in the Steward Health Care System
PARTICIPATING COUNTRIES	U.S.
SUBJECT POPULATION	Male and female patients over the age of 18 with mild to moderately decompensated heart failure not requiring hospital admission for care. Subjects may be enrolled in the study only if all inclusion criteria and none of the exclusion criteria are met.
INCLUSION AND EXCLUSION CRITERIA	
Inclusion Criteria:
 
 1. Age \geq 18 years 2. Symptomatic and chronic heart failure (NYHA Class II and III). 3. Patients on guideline directed medical therapy 90 days prior to enrollment. 4. Adequate home environment for at-home treatment. 5. Presenting or referred to the ER or clinic because of evidence of worsening heart failure with fluid overload (decompensation) 6. A modification in oral diuretics is not clinically appropriate as deemed by the investigator. 7. Estimated excess fluid weight of 4 lbs. or more from euvolemic state. 8. Participant able to give informed consent for participation in trial. Agreeing to sign informed consent and HIPAA authorization. 9. Understanding and willing to comply with the protocols of the trial. 10. Ability of the participant or caregiver to independently apply the investigational device and medication. 
Exclusion Criteria:
 
 1. ACC/AHA Stage D heart failure or patients requiring IV inotrope therapy

	
 2. Massive volume overload (e.g., >20 lbs. of estimated fluid weight) or anasarca. 3. Suspected high risk clinical instability with outpatient treatment. 4. Pregnant females or women of child-bearing age who are not willing to use an adequate form of contraception. 5. Chronic Obstructive Pulmonary Disease (COPD) moderate or worse: FEV1/FCV ratio <0.7 and FEV1 <60 percent predicted. 6. Rapid atrial fibrillation (AF) (HR >100b/min). 7. Hypoxia (resting O₂ saturation <90%). 8. Hypotension (systolic blood pressure (SBP) BP < 90 mmHg). 9. Uncontrolled diabetes mellitus (DM) (admission glucose levels > 300 mg/dL). 10. Advanced renal disease (eGFR < 30mL/min/1.73m²). 11. Acute coronary syndrome. 12. Serum potassium (K⁺) <3.2 mmol/L or > 5.5mmol/L. 13. On experimental medication or currently participating in an interventional cardiovascular research study, other than an observational or registry study. 14. Having received intravenous furosemide within 24 hours prior to enrollment. 15. Urinary tract abnormality or disorder interfering with urination 16. Allergy to the active and inactive ingredients of the study medication. 17. Inability to comply with study requirements. 18. Dementia. 19. Ongoing substance abuse. 20. Concern that the current episode of decompensation was precipitated by a serious medical condition which
--	--

	may require additional evaluation or treatment.
STATISTICAL ANALYSIS	
Primary Outcome
 
Description of treatment effect and as described in the study endpoints.
 
Description of the seriousness, severity, relatedness of all adverse events observed during the study period.

1)

3 INTRODUCTION

3.1 BACKGROUND

Over 650,000 new heart failure cases are diagnosed annually, and it is estimated that one million people get hospitalized per year.¹ Readmission rates at 30 days and 6 months are estimated to be 25% and 50% respectively. Approximately 5 million people in the United States have symptoms or signs of heart failure with a \$30 billion annual cost to the US healthcare system. Hospitals across the country have come up with practical and pragmatic strategies to manage acute decompensated heart failure (ADHF) in the ambulatory setting due to fiscal incentives.^{2,3} The oral bioavailability of furosemide varies from 20% to 90% and in ADHF the absorption of furosemide has been found to be unpredictable.⁴ It is hypothesized that in ADHF, there is “gut edema”, which makes it difficult for the absorption of oral furosemide. Thus, intravenous diuretic therapy has become the cornerstone of the treatment of patients with ADHF. However, intravenous (IV) therapy requires the placement of central or peripheral lines, usually placed and managed by health care practitioners. This is associated with increased maintenance expense, associated patient discomfort, and possible line complications. Also the disposition of patients to home as compared to nursing home rehabilitation facilities can be influenced by the type of IV line placed.

[figure not shown]
Subcutaneous furosemide has been proposed as an alternative to the delivery of parenteral loop diuretics. scPharmaceuticals, Inc (Burlington, MA, USA) has developed a subcutaneous formulation of furosemide injection, Furosemide Injection Solution (SCP-101) with a proprietary infusion pump for this purpose. Commercially produced furosemide USP is alkaline, with a pH of 8.0 to 9.3, and hence could cause irritation of the subcutaneous tissue. The proprietary SC formulation is the first buffered furosemide injection solution, which is isotonic, and has a neutral pH of 7.4. The sc2Wear™ Furosemide Infusor (scPharmaceutical Inc, Burlington, MA) is a two-component design, which combines a reusable component and a cost-effective single-use cartridge (**Figure 1**).

3.2 PRELIMINARY DATA

The sc2Wear™ Furosemide Infusor is designed to deliver a total of 80mg of parenteral furosemide over a period of 5 hours via SC infusion (30mg in hour 1, then 12.5 mg/hour over the next 4 hours). Pivotal pharmacokinetic and pharmacodynamics study evaluating a novel formulation of furosemide have shown 99.6% bioavailability with subcutaneous administration versus intravenous administration of the current parenteral formulation of furosemide. The subcutaneous furosemide formulation was also well tolerated with minimal skin reactions.⁵ Subcutaneous infusion of furosemide has similar bioavailability as intravenous therapy with

therapeutic levels of furosemide achieved within 30 minutes.⁶⁻⁸ Compared to people who got injected with normal saline (control), subcutaneous administration of furosemide was found to increase diuresis in normal volunteers.⁹

Figure 1. The sc2Wear™ Furosemide Infusor.

4 OBJECTIVES

- 1) Evaluate the clinical effectiveness of sc2Wear furosemide Infusor in the in-home management of mild to moderate decompensated heart failure.
- 2.) Evaluate the safety and tolerability of sc2Wear furosemide Infusor in the in-home management of mild to moderate decompensated heart failure.

5 OVERALL STUDY DESIGN

This is a prospective, open-label, two-phase study to evaluate the clinical utility of subcutaneous administration of a novel furosemide formulation. In the first phase of the study (Pilot Phase), the practicality and safety of the novel in-home treatment alternative will be evaluated in 20

patients presenting with mild to moderate ADHF to the cardiology service at St Elizabeth's Medical Center, Brighton, Massachusetts (SEMC).

After completion of the first phase, representatives of the sponsor and scPharmaceuticals will convene to review the experience and results and consider any adjustments to the study or workflow before commencing the Evaluation Phase of the study in which an additional 40 patients will be recruited. Adjustments to the study procedures are subject to IRB review and approval. The Evaluation Phase may involve participation by up to three Steward Health Care System hospitals.

Participants will be treated for 3 consecutive days at home. The sc2Wear™ Furosemide Infusor therapy is intended to be performed by the patient or a lay caregiver. Patients will be homebound during the episode of care for decompensated heart failure. Steward Home Care and Hospice will visit patients daily for home health nursing services. Participants will be visited at home by a visiting nurse who will give them further teaching on the sc2Wear™ Furosemide Infusor. The visiting nurse will also be responsible for obtaining history (symptoms), physical examination (including inspecting the skin for adverse reactions related to the pump), and laboratory draws, supplementation of electrolytes as needed and administration of the dyspnea scale.

Patients will be evaluated by the cardiology service of SEMC within 24 hours of the last dose of the sc2Wear™ Furosemide Infusor. If a patient is found to have satisfactorily responded but requires additional parenteral diuretics an additional 4 days may be prescribed for total of seven consecutive treatments. If additional units are prescribed, patients will be evaluated by the cardiology service of SEMC within 24 hours of the last dose of the sc2Wear™ Furosemide infusion.

Additionally, up to three-sc2Wear furosemide at home treatments may be used as authorized by the treating physician in case the patient experience worsening of heart failure within 30-days of enrollment (Rescue Treatment). Participants will be seen in clinic for follow up at 30 ± 3 days after the start of the study for a post treatment follow up. A Time and Events Schedule is attached as **Appendix A**.

6 STUDY POPULATION AND ELIGIBILITY CRITERIA

The cardiology service at St Elizabeth's Medical Center will screen patients based on the eligibility criteria listed below. Patients who are deemed to qualify for this therapy will be seen at the St Elizabeth's Medical Center cardiology clinic.

6.1 INCLUSION CRITERIA

- Age \geq 18 years
- Symptomatic and chronic heart failure (NYHA Class II and III).
- Patients on guideline directed medical therapy 90 days prior to enrollment.
- Adequate home environment for at-home treatment.
- Presenting or referred to the clinic because of evidence of worsening heart failure with fluid overload (decompensation).
- A modification in oral diuretics is not clinically appropriate as deemed by the investigator.
- Estimated excess fluid weight of 4 lbs. or more from euvolemic state.
- Participant able to give informed consent for participation in trial. Agreeing to sign informed consent and HIPAA authorization.
- Understanding and willing to comply with the protocols of the trial.

Ability of the participant or caregiver to independently apply the investigational device and medication.

6.2 EXCLUSION CRITERIA

- ACC/AHA Stage D heart failure or patients requiring IV inotrope therapy.
- Massive volume overload (e.g., >20 lbs. of estimated fluid weight) or anasarca.
- Suspected high risk clinical instability with outpatient treatment.
- Pregnant females or women of child-bearing age who are not willing to use an adequate form of contraception.
- Chronic Obstructive Pulmonary Disease (COPD) moderate or worse: FEV1/FCV ratio <0.7 and FEV1 <60 percent predicted.
- Rapid atrial fibrillation (AF) (HR >100 b/min).
- Hypoxia (resting O₂ saturation $<90\%$).
- Hypotension (systolic blood pressure (SBP) BP < 90 mmHg).
- Uncontrolled diabetes mellitus (DM) (admission glucose levels > 300 mg/dL).
- Advanced renal disease (eGFR < 30 mL/min/1.73m²).
- Acute coronary syndrome.
- Serum potassium (K⁺) <3.2 mmol/L or > 5.5 mmol/L.
- On experimental medication or currently participating in an interventional cardiovascular research study, other than an observational or registry study.
- Having received intravenous furosemide within 24 hours prior to enrollment.
- Urinary tract abnormality or disorder interfering with urination.
- Allergy to the active and inactive ingredients of the study medication.
- Inability to comply with study requirements.
- Ongoing substance abuse.

- Concern that the current episode of decompensation was precipitated by a serious medical condition which may require additional evaluation or treatment.
- Dementia

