(e) Alcohol Prep Pads for cleaning the top of the medicine Vial and the skin prior to applying the Pump.

(f) The device is adhered to the body using medical grade adhesive 1776 acrylate adhesive manufactured by 3M. The 1776 adhesive is identical to the commercially available 3M Mepitape [Class I, Exempt], except that a liner is added for converting/handling.

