8.1 Buffered Furosemide Injection

Buffered furosemide injection (SCP-101, Furosemide Injection), 10mL of undiluted buffered furosemide solution (8 mg/mL), manufactured by Cook Pharmica, Bloomington, IN, USA under GMP conditions. Contains Tris Hydrochloride, Sodium Chloride and may contain Sodium Hydroxide and Hydrochloric acid for pH adjustment: pH 7.4 (7.0 - 7.8). The sc2Wear furosemide Infusor will be provided by scPharmaceuticals to the investigational site as a starter kit (containing the Activator, cartridge and drug) as well as refill kits containing the drug and cartridge.

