8.2 Labeling

Study drug (Furosemide Injection Solution (SCP-101)) and study device (sc2WearTM Furosemide Infusor) will bear labels that meet applicable laws for an investigational drug-device combination, which may include, but is not limited to, the following information:

- Federal law statement
- Study/Investigator information
- Batch number

- Storage information

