10.2 Safety Endpoints

- The safety of the sc2 Wear furosemide drug-device combination will be assessed by the incidence of adverse events.
- Discontinuation due to presence of skin reaction to drug or device/adhesive.

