11 RISK MANAGEMENT

Furosemide has been available for over five decades and is considered a safe drug. The potential risks related to this study are not different from the risks of any form of diuresis whether inpatient or outpatient. During diuresis, sometimes there are rapid fluid shifts which could lead to electrolyte imbalance or postural hypotension. Subjects will be closely monitored and electrolytes will be supplemented as needed. Patients will be encouraged to avoid rapid postural changes during diuresis and will need to be homebound to ensure their safety.

Patients will be informed of the expected increased urine output. Rarely gout may also be precipitated when fluid is taken out of the body. Dryness of the mouth, thirst, weakness, lethargy, drowsiness, restlessness, muscle pains or cramps, muscular fatigue, hypotension, oliguria, tachycardia, arrhythmia, or gastrointestinal disturbances such as nausea and vomiting will be monitored. There are rare risks of local allergic reaction from the adhesive of the infusor, activation of systemic lupus erythematosus or worsening kidney function in which case the SQ furosemide infusion will be stopped. Patients allergic to sulfa may be allergic to furosemide. Patients with diabetes mellitus should be told that furosemide may increase blood glucose levels and thereby affect urine glucose tests. The skin of some patients may be more sensitive to the effects of sunlight while taking furosemide. Patients may not participate in this study if they are pregnant or plan to be pregnant during the study since the effects of the study device system on an unborn baby are unknown.

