13.4 Device Adverse Events

If the pump falls off during drug infusion or if the needle appears before pump placement there is a risk of needle stick. In this scenario, the pump will need to be handled carefully. Device adverse reactions could include local reaction/skin irritation or redness, allergic reaction to the adhesive agent, and rarely scarring.

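### The allergy exclusion covers the drug but not the infusor's skin adhesive, although the protocol lists adhesive allergy as a product risk and counts discontinuation for it as a safety endpoint

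*Combined protocol and SAP*

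**What the plan says.** Section 6.2 excludes patients with "Allergy to the active and inactive ingredients of the study medication". Exclusion 16 in the synopsis is worded the same way, so it does not widen the rule.

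Section 8.1 gives the composition of the furosemide solution: "Contains Tris Hydrochloride, Sodium Chloride and may contain Sodium Hydroxide and Hydrochloric acid for pH adjustment". Section 8.2 speaks of "Study drug (Furosemide Injection Solution (SCP-101)) and study device" as two things. Among the disposable components, section 8 describes the fixation: "The device is adhered to the body using medical grade adhesive 1776 acrylate adhesive".

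Three other sections deal with the adhesive as a source of harm:

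- Section 11: "There are rare risks of local allergic reaction from the adhesive of the infusor".
- Section 13.4, on device adverse reactions: "local reaction/skin irritation or redness, allergic reaction to the adhesive agent, and rarely scarring".
- Section 10.2, as one of two safety endpoints: "Discontinuation due to presence of skin reaction to drug or device/adhesive".

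Section 14 reports that endpoint as a percentage of subjects, first for the 20 pilot patients and then for all 60.

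**The concern.** The product is a drug-device combination, and the protocol recognises that either half can cause an allergic reaction. Eligibility screens for only one half. A site that follows the criteria literally has no ground to exclude a patient who reports an allergy to medical adhesive, and must then apply that adhesive daily.

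Two things are at stake. The patient is exposed to a reaction that could be foreseen and avoided. And the skin-discontinuation percentage becomes harder to read, because a discontinuation in someone already known to be allergic says little about tolerability in the patients for whom the device would be suitable.

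**Working it through.** **1. What the exclusion covers.** The rule refers to ingredients of the medication. Section 8.1 lists the buffer, the salt and possible pH adjusters in the furosemide solution. The adhesive appears only in section 8, as part of the cartridge and as the means of fixing the device. With drug and device named separately in section 8.2, the plain reading leaves the adhesive outside the exclusion.

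**2. Whether another criterion closes the gap.** None of the other entries in sections 6.1 and 6.2 mentions adhesive, tape, device material or skin allergy. The criteria on clinical instability, on ability to comply and on applying the device independently do not fit an adhesive allergy. Investigator discretion appears in section 6.3, but only as a reason to withdraw a patient already enrolled. Section 9.1 and Appendix A collect medical history but specify no allergy question.

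**3. How a reaction reaches the endpoint.** The section 10.2 endpoint is discontinuation for a skin reaction, not the reaction itself. An adhesive reaction that does not lead to discontinuation counts only as an adverse event. One that does lead to it counts in both safety endpoints.

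**4. Exposure.** Each unit delivers 30 + 4 × 12.5 = 80 mg over 1 + 4 = 5 hours, and the cartridge that carries the adhesive is then discarded. The maximum number of applications is 3 initial + 4 additional + 3 rescue = 10. Contact is therefore repeated and intermittent, about 5 hours of infusion per unit. The first unit stays on somewhat longer, because it is placed in the clinic and activated at home.

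**5. The plan's own figure.** Section 14 says that 59 evaluable subjects suffice to detect, with 95% confidence, an event with an incidence of 5% or more.

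- n = 59: 1 − 0.95^59 = 0.9515
- n = 58: 1 − 0.95^58 = 0.9490
- smallest n: ln(0.05)/ln(0.95) = 58.40, rounded up to 59

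The figure reproduces. It is a general statement about any event, and section 14 does not attach it to skin discontinuation.

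**6. Scale of the effect on this endpoint.** One discontinuation is 1/60 = 1.7 percentage points in the final analysis and 1/20 = 5 points in the pilot. If a share π of enrolled patients has a known adhesive allergy, and a proportion d of them discontinues for it, the expected addition to the reported percentage is π × d. The documents give neither quantity. Purely as an assumption, with d = 1 (the worst case):

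| π (assumed) | Expected patients of 60 | Expected addition |
|---|---|---|
| 0% | 60 × 0 = 0 | 0 points |
| 1% | 60 × 0.01 = 0.6 | 1 point |
| 2% | 60 × 0.02 = 1.2 | 2 points |

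Much larger values of π × d would be hard to square with section 11, which calls the reaction rare.

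**The case against.** The strongest reply is that this is a minor wording gap in a small descriptive study with several safeguards. Wear is short, a barrier film is supplied to protect the skin, the first unit is placed in the clinic, nurses inspect the site at home visits, and section 6.3 allows withdrawal for adverse reactions. Section 13.9 requires a narrative and a causality assessment for each event, so a case with a recorded prior allergy could be described separately. The Instructions for Use, Quick Reference Guide and consent form are not shown and may carry an adhesive warning.

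Much of this stands as mitigation. None of it makes a known allergy a reason for exclusion. The safeguards act after enrolment, the narrative helps only if the allergy was asked about, and the unseen appendices are not the eligibility criteria.

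Some stronger readings are tempting, but the documents do not support them:

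- **That one such enrolment would cost the trial its under-5% conclusion.** The exact one-sided 95% upper bound does move from 4.95% at 0/59 to 7.8% at 1/59. But any single event of any cause does that, and section 14 sets no threshold or bound for skin discontinuation.
- **That one or two such patients should be expected.** No prevalence is given, and the number may be zero.
- **That the safety endpoint is invalidated.** It is a descriptive percentage with event narratives; interpretation is blurred, no more.
- **That every adhesive reaction stops treatment.** The stopping clause in section 11 follows a list of three risks, and it is unclear whether it governs all three. Stopping an infusion is also not defined there as discontinuation.
- **That patients wear the adhesive continuously for days.** The schedule in step 4 shows otherwise.
- **That barrier-film allergy is an equal gap.** Sections 11 and 13.4 name the adhesive only.
- **That the exclusion requires allergy to both active and inactive ingredients.** That is a literalism no screener would apply.

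**Conclusion.** The gap is real. As written, a patient with known allergy to the infusor's adhesive is eligible, while three other sections treat a reaction to the device or its adhesive as a risk or an outcome of the product. This is an inconsistency between eligibility, risk and endpoint text, and it should be corrected.

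The case rests on avoiding a foreseeable reaction and on a clearer endpoint, not on arithmetic. In 60 patients the expected effect on the reported percentage is small: each affected patient adds 1.7 points, and the number is unknown and possibly zero. The conclusion assumes that the medication's ingredients are those listed in section 8.1. It also assumes that sites apply the listed criteria as written and do not add an adhesive question of their own.

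**What to change.** Amend the allergy exclusion identically in section 6.2 and synopsis item 16, for example: *known allergy to any ingredient of the study drug, active or inactive, or to the adhesive that fixes the infusor to the skin*. Other skin-contact items in the kit, such as the barrier film, may be added but are optional. Add one allergy question to the screening history in section 9.1 and Appendix A.

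In section 14, state that the skin-discontinuation percentage applies to patients without known adhesive allergy. Because pilot and evaluation patients are pooled, any patient enrolled before the amendment should be checked for a recorded adhesive allergy and, if one is found, identified in the report.

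The cost is an amendment of a few lines with IRB review, one screening question, very few patients excluded and a slightly narrower population for this endpoint. Sample size and the rest of the analysis are unchanged.
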